### **12.2.1. Suspected Unexpected Serious Adverse Reactions**

Suspected unexpected serious adverse reactions (SUSARs) are AEs that are believed to be related to the trial medication and are both unexpected (i.e., the nature or severity is not expected from the information provided in the Investigator Brochure) and serious.

### **12.2.2. Expected Adverse Events**

Perceived deterioration of IIH necessitating attendance or admission to hospital will not be reported as an SAE, but these events will be reported and recorded at follow-up. Non-protocol LPs will be reported at follow-up.

### **12.2.3. Reporting Serious Adverse Events**

All SAEs occurring during clinical studies must be reported to the appropriate Sponsor designee (contract research organisation) within 24 hours of their knowledge of the event.

SAEs will be reported from the time a signed and dated informed consent form is obtained until completion of the patient's final safety follow-up visit.

Information regarding SAEs will be transmitted to the Sponsor's safety contact using the SAE Form, which must be completed and signed by the Investigator, and transmitted to the Sponsor's safety contact within 24 hours.

The contact details are:

The Sponsor assumes responsibility for appropriate reporting of SAEs or SUSARs to the regulatory authorities. The Investigator (or Sponsor where required) must report these events to the appropriate Independent Ethics Committee (IEC) that approved the protocol unless otherwise required and documented by the IEC.

Study Number: INVEX-CLIN-IIH-301 Protocol	Compound No.: Presendin
	Version: 3.0

An annual safety report will be submitted to the Institutional Review Board once a year via the Investigator.

### **12.3. Reporting and Handling of Pregnancies**

Pregnant patients will be withdrawn from the trial.

Female patients will be instructed to notify the Investigator immediately if they become pregnant during the trial and up to 12 weeks after discontinuation/completion of trial medication. Pregnant patients will be withdrawn from further trial treatment. The patients will also be instructed to report pregnancies discovered after the last visit, if they believe that conception occurred during their participation in the trial.

A pregnancy as such is not an AE, unless there is a possibility that the trial medication has interfered with the efficiency of any contraceptive measures. The Investigator should report all pregnancies to the Sponsor contact or designee within 24 hours of being informed of them. The pregnancy report form should be used instead of the SAE form.

The pregnant patients will be followed until the end of the pregnancy. Any complication during the pregnancy should preferably be reported as an AE. The outcome of the pregnancy must be reported on the pregnancy report form. Any spontaneous abortion, stillbirth, birth defect/congenital anomaly, death, or other serious infant condition must be reported and followed up as an SAE.

Patients will give consent on enrolment that the Investigator will report any pregnancy to the Sponsor and that further information will be collected until delivery.

Study Number: INVEX-CLIN-IIH-301 Protocol	Compound No.: Presendin
	Version: 3.0

## 13. DATA ANALYSIS AND STATISTICAL CONSIDERATIONS

The Statistical Analysis Plan (SAP) will be finalised prior to database lock providing detailed methods for the analyses outlined below.

### 13.1. Hypotheses

This trial compares outcomes in IIH patients under Presendin and matched placebo. The primary hypothesis that will be tested is:

- The ICP measurement in the Presendin group is equal to the ICP measurement in the placebo group at Week 24; against the alternative that the outcomes differ

### 13.2. Trial Design Considerations

#### 13.2.1. Sample Size Assumptions

The target sample size for the trial is 240 randomised patients, i.e., 120 patients per arm. We justify this figure in the following sections. The two outcomes for which we sought to power the study are ICP and PMD.

##### 13.2.1.1. Intracranial Pressure Power

The most difficult parameters to specify for a sample size calculation pertain to the variability of outcomes. We present a brief summary of the literature. Baseline standard deviations (SD) of ICP in previous trials were: 5.4 (n=10) and 6.3 (n=17) in the Drug Trial [Markey, 2017]; 5.0 (n=16) (data on file); and 5.7 (n=32) and 5.3 (n=30) in the Weight Trial [Ottridge, 2017]. Post-baseline standard deviations were slightly lower (and less than 6.0) in three of these five arms; and increased slightly in one (but remained less than 6.0). The post-baseline standard deviation however increased to over 8.0 in the surgery arm of the Weight Trial because the surgical intervention dramatically impacted ICP in some patients. In the NORDIC trial [Wall, 2014] however, the standard deviation of baseline ICP was much higher, at 9.4 in the treatment arm (n=86). Seeking to avoid underpowering the study, we elected to proceed with the SD estimate for the NORDIC trial as this is the most similar trial population to the planned IIH EVOLVE trial (both recruiting acute IIH). We assume that control arm baseline and 24-week ICP SD equals 9.4, Presendin baseline ICP SD equals 9.4, and Presendin 24-week ICP SD equals 10.4. These values assume the variability of ICP measures in untreated patients is as high as has been seen in the NORDIC trial and assumes that the variability in treated patients is slightly higher still. We anticipate that the standard deviation will be slightly higher in the experimental arm as treatment effects will potentially manifest changes in ICP. However, we do not expect such variability to be as inflated in this trial relative to control as it was

Study Number: INVEX-CLIN-IIH-301 Protocol	Compound No.: Presendin
	Version: 3.0

in the Weight Trial because of the likely difference in treatment effect between surgical and drug interventions.

Under this parameterisation, when testing for a difference between arms at 24-weeks of 5 CSF (justified below) using a total sample size of 240, assuming that up to 50% of observations are missing (i.e. 60 final LPs are completed in each arm), using a 5% significance level by Analysis of Covariance (ANCOVA) adjusted for baseline ICP, the two stratification variables, and treatment arm, we expect to have approximately 85% power. If 40% of observations are missing (i.e. 72 final LPs are completed in each arm), we expect power to be 91%. These figures have been inferred by computer simulation. Of the 165 patients in IIHTT [Wall, 2014] it was reported that “only 85 participants (47 [55%] in the [treated] group and 38 [48%] in the placebo group) agreed to a lumbar puncture at month 6.”

We expect a high rate of missing data because lumbar puncture is an invasive procedure that patients can find painful and traumatising [Scotton, 2018]. If patients have an unpleasant experience at the diagnostic LP they are also more likely to decline the LP at trial outcome. If patients do decline the final LP, logically it will be because of the baseline experience rather than their prevailing ICP. If data for the LP at 24 weeks is missing, the reason will be recorded.

Outcomes from previous trials show that baseline and post-baseline distributions of ICP show central tendency with approximate symmetry, so we conclude that normality is a reasonable assumption and therefore ANCOVA is a defensible analysis method.

### 13.2.1.1. Perimetric Mean Deviation Power

We summarise here the estimated power for detecting differences between arms in the PMD outcome measure. In the NORDIC trial [Wall, 2014], the authors observed that the improvement from baseline to 6-months in PMD was 0.71dB greater in the experimental arm than the control arm. Cross-sectional SD of PMD was 1.1-1.2 at baseline. Table 2 in their publication shows that the standard error of mean PMD is higher at 6m than at baseline, likely reflecting a combined effect of missing data at 6-months and greater variability of post-baseline measures. We plan to take repeated measures of PMD at baseline, 2 weeks, 1-month (m), 2m, 3 m, 4m, 5m and 6m. Assuming that the overall SD of PMD scores is 1.8, thus introducing some reasonable inflation on Wall *et al.*'s baseline variability parameter for the reasons identified, using the formula given on p.31 of Diggle, Liang & Zeger (1994) we would expect to require 142 patients in total to detect a difference of 0.71dB (justified below) with 90% power at a 5% significance level, if the serial correlation between repeated measures is 0.4 (and we expect a value in this region) [Diggle, 1994]. If the serial correlation parameter is as low as 0.3, the required sample size increases to 166.

Study Number: INVEX-CLIN-IIH-301 Protocol	Compound No.: Presendin
	Version: 3.0

Note that the method used above assumes full follow-up and data collection. Although every effort will be made to collect all outcomes, naturally some missing data is expected. If we inflate the maximum sample size identified above by up to 30% to account for some data loss, we require up to  $166 / 0.7 = 237$  patients. The assumed 30% missing data rate was adjudged to be realistic by the Sponsor based on previous trials in IIH. Thus, we expect to be able to cover the impact of missing data using the extra patients necessitated by the sample size calculation for ICP.

The above assumes only one eye is measured per patient. In actuality, some patients may provide outcomes for both eyes because any eye that satisfies the eligibility criteria (see Section 5.2) will be enlisted in the study. Put another way, all patients will provide outcomes in at least one eye, and some will provide outcomes in two. Second eyes will naturally be highly correlated with first eyes. From a sample size perspective, this means the additional information in second eyes will be of modest value. Nevertheless, outcomes on second eyes will contain some additional information and should be included in the analysis in the interest of efficiency. When estimating sample size, for the sake of simplicity and because of uncertainty in the rate of eligibility in second eyes, we have assumed that each patient yields outcomes from only one eye. Eligible second eyes will be included in the analysis with appropriate model terms to handle the within-patient correlation (further details are included in the SAP). As such we expect outcomes from second eyes to provide a modest uplift in power to the scenarios presented here.

This section assumes a longitudinal analysis method such as hierarchical regression.

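### The PMD sample sizes 142, 166 and 237 match only a one-sided 5% test; at two-sided 5%, 240 patients with 30% loss give about 84–89% power, not 90%

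*Protocol*

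**What the plan says.** Section 13.2.1 names ICP and PMD as the two outcomes on which the trial is powered, and section 13.3.1.5 treats PMD as the initial secondary endpoint. The PMD calculation is in the second subsection numbered 13.2.1.1, Perimetric Mean Deviation Power (v3.0).

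- Effect: in the earlier acetazolamide trial, "the improvement from baseline to 6-months in PMD was 0.71dB greater in the experimental arm than the control arm".
- Variability: "Assuming that the overall SD of PMD scores is 1.8", against 1.1–1.2 observed at baseline in that trial.
- Schedule: "We plan to take repeated measures of PMD at baseline, 2 weeks, 1-month (m), 2m, 3 m, 4m, 5m and 6m".
- Result: "we would expect to require 142 patients in total to detect a difference of 0.71dB (justified below) with 90% power". The error rate and correlation are given as "with 90% power at a 5% significance level, if the serial correlation between repeated measures is 0.4".
- Low-correlation case: "If the serial correlation parameter is as low as 0.3, the required sample size increases to 166".
- Data loss: "If we inflate the maximum sample size identified above by up to 30% to account for some data loss", computed as 166 / 0.7 = 237. The section concludes that the patients already needed for ICP cover this.

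The formula is cited to a page of a longitudinal-data textbook and is not written out. Sidedness is not given for PMD. The only hypothesis written down is the primary one for ICP, in section 13.1: equality "against the alternative that the outcomes differ".

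**The concern.** The section gives every input that a repeated-measures sample size needs, so its figures can be checked. They agree with a one-sided 5% test. A one-sided 5% test is a two-sided 10% test, twice the error rate that a reader would take from an unqualified 5% beside a non-directional primary hypothesis.

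At stake is the closing claim of the section: that 240 patients still give 90% power for PMD when the correlation is as low as 0.3 and 30% of the data are lost. A regulator or statistical referee can test that claim from the protocol alone.

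**Working it through.** **Inputs**, all from the PMD power section: times 0, 0.5, 1, 2, 3, 4, 5, 6 months; SD 1.8; difference 0.71 dB at 6 months; power 90% (z = 1.2816); correlation rho = 0.4 or 0.3; data loss 30%. Planned N is 240, allocated 1:1 (section 13.2.1).

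**Formula** for a difference in rate of change with equal correlation between visits:

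N total = 4 (z_alpha + z_power)² × SD² × (1 − rho) / (Sxx × d²)

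- Sxx = 91.25 − 21.5²/8 = 33.47 (sum of squared deviations of the visit times).
- d = 0.71/6 = 0.1183 dB per month, so Sxx × d² = 0.4687.
- SD² (1 − rho) = 3.24 × 0.6 = 1.944 at rho 0.4, and 3.24 × 0.7 = 2.268 at rho 0.3.

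**Reproducing the protocol's figures, z_alpha = 1.645.** (1.645 + 1.2816)² = 8.564.

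- rho 0.4: 4 × 8.564 × 1.944 / 0.4687 = 142.1 (71.05 per arm). Stated: 142.
- rho 0.3: 4 × 8.564 × 2.268 / 0.4687 = 165.8 (82.89 per arm). Stated: 166.
- 166 / 0.7 = 237. Stated: 237.

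**The same with z_alpha = 1.960.** (1.960 + 1.2816)² = 10.507.

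- rho 0.4: 174.3 (87.17 per arm), so 88 per arm and 176 in total.
- rho 0.3: 203.4 (101.70 per arm), so 102 per arm and 204 in total.
- After 30% loss: 176/0.7 = 251.4 and 204/0.7 = 291.4, or 252 and 292 with equal arms.

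**Is the formula identified correctly?** Protocol v1.0 gives a second, superseded set, used here only to identify the method: visits at 0, 2, 4, 6 months, SD 1.5, 138 patients at rho 0.5 and 192 at rho 0.3. The slope formula with 1.645 gives 137.6 and 192.6 (68.8 and 96.3 per arm, rounding to 69 and 96). With 1.960 it gives 168.8 and 236.4. All four stated sizes match the one-sided value after rounding per arm, and none matches the two-sided value.

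Other contrasts were tried: a time-averaged difference, change from baseline, ANCOVA on the post-baseline mean, and slopes on other visit sets. None gives the pair 142 and 166 at two-sided 5%. The time-averaged formula also moves the wrong way: its two-sided N falls from about 128 at rho 0.4 to about 105 at rho 0.3, whereas the protocol's N rises. A two-sided slope test fits 142 and 166 only at about 83% power.

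**Two-sided power for the slope difference**, Φ(√[N × Sxx × d² / (4 SD² (1 − rho))] − 1.960):

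| N with complete data | rho 0.4 | rho 0.3 |
|---|---|---|
| 142 | 83.3% | 77.3% |
| 166 | 88.6% | 83.4% |
| 168 (= 240 × 0.7) | 88.9% | 83.8% |
| 240 (no loss) | 96.7% | 94.1% |

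**The case against.** **Sidedness is inferred.** The non-directional alternative in section 13.1 belongs to the primary ICP hypothesis; nothing shown fixes it for PMD. That is fair. The published ICP powers of 85% and 91% do not settle it either, because the baseline correlation behind them is not given: two-sided with an assumed correlation of 0.4 yields 85.4% and 91.0%, and one-sided with none yields 86.8% and 91.6%. Two-sided remains the natural reading of an unqualified 5%. If one-sided was meant for PMD, it is undeclared and the section still needs correcting.

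**The shortfall is confined to a pessimistic case.** This stands in part. A reader might infer that 240 patients cannot deliver 90% power for PMD at all. The figures do not support that: with full follow-up 240 gives 94–97%, and at the expected correlation of 0.4 with 30% loss the gap is about one percentage point. The SD of 1.8 is also well above the 1.1–1.2 seen at baseline in the earlier trial; at 1.62 the two-sided requirement at rho 0.3 is 203.4 × (1.62/1.8)² = 164.8, inside the 168 left after loss. Section 13.2.1.1 expects a modest, unquantified gain from second eyes. Counting 30% missing data as 30% of patients lost ignores partial follow-up that a longitudinal model would use. These points soften the consequence but do not make 142, 166 or 237 right at two-sided 5%.

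**The contrast.** A reader might infer that a slope calculation contradicts the PMD estimand, a difference over 24 weeks. It does not: a slope across the visits is compatible with that wording and with the hierarchical regression that the power section assumes. Under a time-averaged contrast the trial would be amply powered, at about 96–98% two-sided with 168 evaluable. Nor should power be judged on a Week 24 ANCOVA for PMD. No section shown plans one; ANCOVA is specified for ICP.

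**Version.** The calculation is in v3.0. Only closing appendices of v4.0 are shown, so a later correction cannot be excluded.

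**Conclusion.** The point holds in bounded form. The figures 142, 166 and 237 come from the slope formula with a one-sided 5% critical value. At two-sided 5% and 90% power they become 176, 204 and 292. The claim that 240 patients cover rho 0.3 with 30% loss at 90% power therefore fails: power is about 84% there, and about 89% at rho 0.4.

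This rests on the protocol's own SD, effect, visits, correlations and loss rate, on equal correlation between visits, and on reading the PMD test as two-sided. It does not show that the trial is too small, that the PMD estimand is mis-specified, or that the primary ICP power is wrong. It is a misstatement of power for a secondary outcome that the protocol says it was powered on. It should be corrected, without any change to the design.

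**What to change.** Check first whether v4.0 still carries these figures. If it does, amend the PMD power section as follows:

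- State that the PMD test is two-sided at 5%.
- Replace 142 with 176, 166 with 204, and 237 with 292. The matching inflated figure at rho 0.4 is 252.
- Replace the statement that the ICP sample size covers the loss with the power it provides: about 84% (rho 0.3) to 89% (rho 0.4) with 240 patients and 30% loss, and 94–97% with full follow-up.
- Say that the calculation is for a difference in slopes amounting to 0.71 dB over 6 months.

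The cost is a few sentences and a slightly less favourable stated power. No added patients and no change to visits or data collection are needed.

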### **13.2.2. Stratification**

At the outset, it is expected that markers of disease severity will be prognostic of potential efficacy. For this reason, it is proposed to stratify randomisation by, baseline ICP (<35cm or  $\geq 35$  cm), baseline body mass index (< 30 kg/m^2 or  $\geq 30$  kg/m^2) and baseline PMD (worse than or equal to -3.5dB or better than -3.5dB).

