## 1. INTRODUCTION

### 1.1. Background and Rational

Idiopathic intracranial hypertension (IIH) is a condition characterised by raised intracranial pressure (ICP) with unknown aetiology, occurring most frequently in obese women of childbearing age. IIH is a rare condition; however, incidence is increasing with rising obesity trends [Mollan, 2019a]. There is a high rate of repeat hospital admission in IIH (increased by 446% in last decade), reflected in escalating healthcare costs (in England £462 million/year predicted by 2030 [Mollan, 2019a] and more than \$444 million in the USA [Friesner, 2011]).

The cause of IIH is not fully understood. Recent research suggests that IIH is a disease of systemic metabolic dysregulation characterised by central adiposity [Hornby, 2017], double the risk of cardiovascular disease in excess to that mediated by obesity [Adderley, 2019] and dysfunctional adipocyte metabolism primed for weight gain [Westgate, 2021]. Patients are also insulin resistant and have a unique hormone signature of androgen excess both systemically and in the cerebrospinal fluid.[O'Reilly, 2019]

Morbidity in IIH is due to the elevated intracranial pressure which can cause severe papilloedema (swelling of the optic nerve) which can ultimately lead to blindness. The risk of permanent visual loss is a major concern in IIH. Visual loss occurs in greater than 90% of those with IIH [Wall 1991] and can be severe and permanent in between 5-25%. Headache is an additional major disabler and affects the majority of IIH patients (over 90%) [Yri, 2014; Markey, 2016; Mulla 2015] in the long term. Headaches significantly reducing quality of life [Mulla, 2015; Digre, 2015] are driven by raised intracranial pressure and often have a migraine- like phenotype (> 90%) [Mollan 2021a].

Existing pharmacotherapies are limited. The most frequently used drug therapy, acetazolamide, is used off label and has been shown to have efficacy but due to side effects and treatment failures new drugs are needed. [Piper, 2015; Mollan, 2018; Hoffmann, 2018]. Surgical therapy to lower ICP is a last resort and used as an emergency procedure to save vision but there is a high failure rate and frequent complications. The lack of licenced or targeted treatments in IIH perpetuates poor outcomes for patients. A priority setting exercise was run by patients with IIH (James Lind methodology) [Mollan, 2019c] establishing effective therapy was the top priority from the patient group.

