#### **5.2. Eligibility Criteria**

##### **5.2.1. Inclusion Criteria**

Patients must not be enrolled unless they meet all the following criteria:

1. Age  $\geq 18$  years at the time of consent
2. Diagnosis of new IHH by consensus criteria (see Section 16.1, Appendix 1), including normal structural brain imaging (excluding features of raised intracranial pressure and incidentalomas), including either magnetic resonance venography or computed tomographic venography to exclude thrombosis and no evidence of a secondary causes of raised intracranial pressure
3. Newly diagnosed patients with screening commenced no more than 4 weeks after the diagnostic LP
4. Lumbar puncture opening pressure  $\geq 25$  cm cerebrospinal fluid (CSF) at diagnosis
5. Presence of bilateral papilloedema (Frisén grade  $\geq 1$ ). Verification of papilloedema by the OCT Reading Centre. Where there is uncertainty fundus photography and/or ultrasound scan (B scan) of the optic nerves should be conducted for evaluation by the Independent Adjudication Committee (IAC)
6. Perimetric Mean Deviation (PMD) defined as between -2 to -7 decibels (dB) in at least one eye. Eyes meeting this criteria will be defined as ‘study eyes’

Study Number: INVEX-CLIN-IIH-301 Protocol	Compound No.: Presendin
	Version: 3.0

7. Reproducible visual loss present on automated perimetry including no more than 15% false positive responses, (reliability confirmed by the Visual Field Reading Centre) in study eyes
8. Two or more headache days over the 7-day period prior to screening and also the patient must meet this criterion during the 7-day screening period
9. Females of childbearing potential must have a negative pregnancy test and must agree to use a highly effective birth control method (failure rate less than 1% per year when used consistently and correctly – see Section 16.7, Appendix 7 for further details) during the whole trial duration including the last follow-up visit (12 weeks after ceasing drug). Female patients who are lactating must agree to stop breast-feeding. Or female patients of non-childbearing potential (defined as pre-menopausal females with a documented tubal ligation or hysterectomy; or post-menopausal females defined as 12 months of amenorrhoea [in questionable cases a blood sample with simultaneous follicle stimulation hormone (FSH) 25-140 IE/L and oestradiol <200 pmol/L is confirmatory])

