### 13.3.3. Treatment Comparisons

Treatment comparisons will be undertaken between active and control groups. The primary outcome will be analysed as described in Section 13.2.1.

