#### **13.3.6. Missing Data**

Although every effort will be made to collect responses from all patients at all scheduled time points, there undoubtedly will be some missing data. The SAP describes in detail steps for dealing with missing data using relevant imputation strategies for specific endpoints that adjust for treatment arm, centre, baseline value, and stratification variables.

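### The stated primary ANCOVA and imputation take BMI in only as a stratum cut at 30 kg/m²; naming measured baseline BMI as a continuous covariate would be a small, nearly free improvement

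*Protocol*

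**What the plan says.** All references are to protocol v3.0.

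- Section 13.2.2 stratifies randomisation because indicators of severity are expected to be prognostic. It lists three factors: baseline ICP cut at 35 cm, "baseline body mass index" cut at 30 kg/m², and baseline PMD, "worse than or equal to -3.5dB or better than -3.5dB".
- Section 13.2.1.1 describes the ICP test as made "by Analysis of Covariance (ANCOVA) adjusted for baseline ICP, the two stratification variables, and treatment arm".
- Section 13.3.3 makes that the primary analysis: "The primary outcome will be analysed as described in Section 13.2.1".
- Section 13.3.6 says the imputation strategies "adjust for treatment arm, centre, baseline value, and stratification variables".

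Neither model names measured BMI, and the ICP model does not name measured PMD. Table 1 schedules weight, BMI and perimetry for every patient at screening and at baseline, so the measured values will exist.

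**The concern.** Section 1.1 describes the disease as "occurring most frequently in obese women of childbearing age". A cut at 30 kg/m² in such a population should put most patients on one side, and an indicator that hardly varies can explain little. BMI differences between the arms within the large upper stratum, from 30 to well above 40, would go unadjusted.

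Precision matters here because Section 13.2.1.1 allows for up to half of the final lumbar punctures being missing. That leaves 60 per arm for the ANCOVA and puts weight on the imputation model. What is at stake is some efficiency in the primary comparison and some quality in the imputed ICP values.

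**Working it through.** **Inputs.** BMI mean 38.1, SD 6.2 kg/m² (Section 1.1.3, the phase 2 trial, 15 randomised). BMI cut 30 (13.2.2). From 13.2.1.1: Week 24 ICP SD 9.4 on placebo and 10.4 on Presendin, difference 5 cm CSF, 60 or 72 completed lumbar punctures per arm, 5% level. The hypothesis in 13.1 is two-sided. Assumed because not stated: normal BMI, the correlation ρ of baseline with Week 24 ICP, and the partial correlation r of BMI with Week 24 ICP given baseline ICP.

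**1. The plan's own power.** Pooled SD = √((9.4² + 10.4²)/2) = 9.91. Adjusting for baseline ICP multiplies it by √(1 − ρ²). With ρ = 0.4 the residual SD is 9.91 × √0.84 = 9.09, and two-sided power is 85.4% at 60 per arm and 91.0% at 72. The protocol states about 85% and 91%, so both reproduce. With ρ = 0 they would be 78.9% and 85.7%, so a ρ of about 0.35-0.40 is inferred.

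**2. The BMI split.** (30 − 38.1)/6.2 = −1.306, and Φ(−1.306) = 0.096. About 9.6% fall below 30, which is 0.096 × 240 ≈ 23 patients.

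**3. Information kept by the cut.** For a normal variable, the squared correlation between the indicator and the measured value is φ(z)²/(p(1 − p)) = (0.170/0.294)² = 0.33. A median split would keep 0.64.

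**4. Sensitivity of steps 2 and 3.**

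| Assumed BMI | Share below 30 | Information kept |
|---|---|---|
| Normal, mean 38.1, SD 6.2 | 9.6% | 0.33 |
| Normal, mean 36-40, SD 5-8 | 2-23% | 0.13-0.52 |
| Normal, mean 34-35, SD 5-8 | 16-31% | 0.44-0.58 |
| Lognormal, mean 38.1, SD 6.2 | 8% | 0.24 |

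**5. What measured BMI would add.** Extra residual variance removed = r² × (1 − 0.33). Equivalent gain in sample = (1 − 0.33r²)/(1 − r²) − 1. Power is at 60 per arm with ρ = 0.4.

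| r (assumed) | Extra variance removed | Sample gain, of 120 readings | Power, cut | Power, measured |
|---|---|---|---|---|
| 0 | 0% | 0 | 85.4% | 85.4% |
| 0.1 | 0.7% | 0.7% (about 1) | 85.5% | 85.8% |
| 0.2 | 2.7% | 2.8% (about 3) | 85.9% | 86.8% |
| 0.3 | 6.0% | 6.6% (about 8) | 86.4% | 88.5% |

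**6. Cost.** Putting the measured value in place of the indicator uses the same number of model terms. Adding two measured covariates beside the strata, when neither is prognostic, inflates the variance by about 114/112 = 1.018. Power falls from 85.4% to 84.8%, or about 0.6 point.

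**7. PMD.** Eligibility requires PMD "between -2 to -7 decibels (dB) in at least one eye". The cut at −3.5 dB keeps about 0.63 of the information if PMD is uniform on that range, and 0.47-0.68 for truncated normals with SD 1.1-1.2. Less is lost than with BMI.

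**The case against.** The strongest reply is that the form of a covariate belongs in the SAP, to which the protocol defers for detail, and that adjusting for the factors used in randomisation is a defensible default. This stands in part. The SAP is not shown, and neither is the statistics section of v4.0, of which only appendices are available; either may already specify measured values. But v3.0 does state the covariates of both models and does define the stratification variables as cuts, so this concerns stated wording, not omitted detail.

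A second reply is that 13.2.1.1 speaks of two stratification variables while 13.2.2 lists three. Taking the two to be BMI and PMD, with ICP entered as measured, is natural but is an inference: v1.0 uses the same phrase with four factors. That stands too, and is itself a reason to name the covariates.

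A reader might go further and infer that the trial will split 10:90 on BMI, that two thirds of BMI's value is lost, and that recovering it is worthwhile and costs nothing. The documents do not support this. The split rests on 15 patients plus normality, while 13.2.1.1 names a different trial as the closest population and gives no BMI distribution from it. No BMI limit applies at entry. The protocol links weight loss to falls in ICP (13.3.1.1.3), which makes baseline BMI a plausible predictor of Week 24 ICP but does not show that it is one. Nor does the one-third figure carry over to PMD.

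**Conclusion.** The point holds as a minor improvement. As worded in v3.0, the primary ANCOVA and the imputation use BMI through a cut that probably leaves one stratum small and keeps about a third of the information in a linear term (0.13-0.58 over the range examined). The gain from the measured value runs from nothing to about 6% of residual variance, or 0 to 2 points of power at 60 per arm, for partial correlations of 0 to 0.3. That range is assumed, and a linear BMI effect is assumed with it. The planned analysis is not biased or invalid as it stands, and its stated power does not depend on this change.

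**What to change.** Leave the randomisation strata as they are. In 13.2.1.1/13.3.3 and in 13.3.6, list the covariates by name, which also settles two against three, and enter measured baseline BMI (kg/m²) as a continuous covariate beside measured baseline ICP. Measured baseline PMD (dB) may be entered in the ICP model in the same way. Since a patient can have two study eyes, use the eye that defines the PMD stratum and say so. Settle this before unblinding, and make the protocol and SAP agree.

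The cost is wording only: no new data, and no degrees of freedom if the measured values replace the indicators. Keeping the strata as well costs about half a point of power if the measured values turn out not to be prognostic.
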